ARUBA Study

A Randomized trial of Unruptured Brain Arteriovenous malformations

A Randomized Multicenter Clinical Trial of Unruptured Brain AVMs (**ARUBA**)

Clinical Protocol

Sponsors National Institute of Neurological Disorders and Stroke
National Institutes of Health

Number of Patients 800

Trial Leadership [name], M.D. (PI, CCC)
[name]. (PI, DCC)
[name]. (Co-PI, DCC)
[name], (Co-PI, DCC)
[name]. (Co-PI, DCC)
[name]. (Co-PI, CCC, Europe)
[name]. (Co-PI, DCC, Europe)
[name] [name]. (Co-PI, NINDS)

Design Randomized Multicenter Clinical Trial of Unruptured
Brain AVMs

Version Date November 1, 2006

Version **2.1**

Data Coordinating Center: International Center for Health Outcomes and Innovation Research (InCHOIR)

Columbia University, [name]

Phone: [name] ; Fax: [name]

[name], Project Leader, Email: [contact]

Clinical Coordinating Center: Doris & Stanley Tananbaum Stroke Center, Columbia University Medical Center, Department of Neurology

[name]

Phone: [name], Fax: 1+ [contact]

[name] (Coordinator), Email: [contact]

Coordinating Center (Europe): CHU Hôpital Lariboisière, Service de Neurologie, [name]

[contact], [contact]

[name] (Clinical), Email: [contact]

[name] (Data), Email: [contact]

Unite de Recherche Clinique, Hôpital Fernand Widal

[name]

[contact] ; [contact]

PRÉCIS

Study Title

A Randomized Multicenter Clinical Trial of Unruptured Brain AVMs (ARUBA)

Objectives

Primary: To determine whether medical management improves long-term outcomes of patients with unruptured BAVMs compared to interventional therapy (with endovascular procedures, neurosurgery, or radiotherapy, alone or in combination). The trial has been designed to test whether medical management or interventional therapy will reduce the risk of death or stroke (due to hemorrhage or infarction) by at least 40% (an absolute magnitude of about 7.5% over 5 years). It will require 800 patients to detect the hypothesized 40% reduction in event rate, analyzed using the intention-to-treat principal. This sample size will support a test of non-inferiority if the medical management is not superior to interventional therapy.

Secondary: To compare the impact of medical management to interventional therapy with respect to adverse events, quality of life and cost.

Design and Outcomes

The study design is a prospective, multi-center, parallel design, randomized, controlled trial. Treatment assignment will not be masked; however, clinical coordinating center personnel and outcome events committees will be blinded to treatment assignment. Interim study results will be kept confidential by the DCC. The primary outcome is the composite event of death from any cause or stroke (hemorrhage or infarction revealed by imaging). Functional outcome status will be measured by the Rankin Scale, a widely-used outcome measure for stroke. The secondary measures of outcome include adverse events, quality of life and cost.

Interventions and Duration

The interventional therapy arm of the trial involves prophylactic efforts with a plan for eradication of the observed BAVM utilizing endovascular procedures, microsurgery, or radiosurgery, alone or in combination with pharmacological therapy for existing risk factors and coexisting medical conditions. The medical management arm will involve pharmacological therapy as deemed appropriate for medical symptoms as determined by the treating investigator. Should patients in the medical management arm develop hemorrhage or infarction related to their BAVM, they would then be candidates for any single or combination of interventional therapy using endovascular procedures, microsurgery and radiosurgery. Patients will be followed for a minimum of 5 years and a maximum of 7.5 years (mean 6.25 years) from randomization.

Sample Size and Population

All patients with an unruptured BAVM diagnosed at a participating clinical center without prior interventional therapy to attempt eradication and with no contraindications to interventional therapy, will be candidates for this trial. A total of 800 patients will be enrolled in the ARUBA trial. Patients may be referred for enrollment by their clinical neurologist, neurosurgeon, or interventional radiologist.

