The *primary null hypothesis* is that there is no difference between medical management and interventional therapy in the time to stroke or death from any cause. The null hypothesis will be tested against the alternative hypothesis that there is a difference between treatments with a two-sided 0.05 level log-rank test. With a plan to enroll 800 patients, the test will have 87.5% power to detect a risk reduction of 40% (hazard ratio of 0.60), and 80% power to detect a risk reduction of 36.5% (hazard ratio of 0.635). These hazard ratios correspond to an absolute decrease in 5-year event rates of 7.5% and 6.7% respectively for medical management, from an assumed 5-year event rate of 20% for interventional therapy.

If the null hypothesis is not rejected, a test of non-inferiority of medical management compared to interventional therapy will be performed. The null hypothesis for the test of non-inferiority is that the hazard ratio for the composite event of death from any cause or stroke for interventional therapy compared to medical management is less than 0.89 (an 11% reduction in risk for interventional therapy). Thus, the null hypothesis that medical management is inferior will be rejected, and non-inferiority claimed, if the reduced risk of interventional therapy compared to medical management is less than the non-inferiority margin of 11% (hazard ratio ≥ 0.89) based on a one-tailed 0.05 level test. An 11% reduction in risk corresponds to an absolute difference in 5-year event rates of 2%.

The *secondary hypothesis* to be tested is that early intervention decreases the risk of death or clinical impairment at 5 years post-randomization. Death in this young, and otherwise healthy, population is a rare event. The primary hypothesis has been constructed to be inclusive of all strokes that occur during the course of the trial (thereby averting judgment about severity), while the secondary hypothesis concentrates only on those events associated with impairment.

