3. STUDY DESIGN

1. The overall purpose of this multi-center RCT is to evaluate the effectiveness and safety (in terms of survival, clinical impairment, adverse events and quality of life), and costs of medical management compared to interventional therapy of patients with unruptured BAVMs. While the nature of the treatments precludes blinding of patients and their treating clinicians, outcome evaluations should be done by an experienced person who is not directly involved in providing the interventional procedure. Therefore a neurologist at each site who is certified to perform the Rankin assessment will do so for all outcome assessments at that center. A parallel groups design with random assignment of patients to interventional therapy or medical management with equal probability will be performed. A total of 800 patients will be randomized. Patients will be followed for a minimum of 5 years and a maximum of 7.5 years (mean 6.25 years) from randomization.

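### 800 patients do not support the fallback non-inferiority test: power against the 0.89 margin is about 20% if the two strategies are truly equal

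*Protocol*

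**What the plan says.** The Précis (Objectives, Primary) gives 800 patients as the number needed to detect a 40% reduction in event rate and then adds: "This sample size will support a test of non-inferiority if the medical management is not superior to interventional therapy". Section 1.1 lists non-inferiority as Specific Aim 1.1b under the primary hypothesis, to be examined if superiority is not shown.

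The hypothesis paragraphs that follow the list in section 1.2 define both tests. For superiority, the alternative is that "there is a difference between treatments with a two-sided 0.05 level log-rank test"; with 800 patients "the test will have 87.5% power to detect a risk reduction of 40% (hazard ratio of 0.60), and 80% power to detect" a 36.5% reduction (hazard ratio 0.635), "from an assumed 5-year event rate of 20% for interventional therapy". For the fallback, the protocol sets a "non-inferiority margin of 11% (hazard ratio ≥ 0.89) based on a one-tailed 0.05 level test", and equates this margin with 2 percentage points at five years. The supplied text gives no power, event count or assumed true effect for the fallback.

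Section 3 supplies the remaining inputs: "A total of 800 patients will be randomized", with "random assignment of patients to interventional therapy or medical management with equal probability", and follow-up from 5 to 7.5 years (mean 6.25).

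**The concern.** The sentence in the Précis describes a property of the design. Coming straight after the sample-size requirement, it can only mean that 800 patients are enough for the fallback test. Yet the margin is narrow (11% on the hazard scale) and the trial was sized for a 40% reduction, so the two are unlikely to fit together.

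If superiority is missed, Aim 1.1b is the only route by which the protocol can reach a positive statement for medical management on the primary composite endpoint. The cost-effectiveness question in section 1.2 (item 5) is also conditioned on a finding of non-inferiority. If the test usually fails even when the strategies are identical, anyone relying on the Précis is misled about what the trial can show, and a failed test could be misread as evidence that medical management is worse.

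**Working it through.** **Inputs from the protocol.** 800 patients, 1:1; 20% five-year event rate under interventional therapy; follow-up 5 to 7.5 years; margin HR 0.89 (interventional/medical); one-tailed 0.05.

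**Assumptions added here.** Exponential survival, uniform entry (so uniform follow-up between 5 and 7.5 years), no loss to follow-up. Ignoring loss favours the protocol.

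**Step 1: reproduce the stated superiority power.** Expected events are 158.8 at HR 0.60 and 162.1 at HR 0.635. Freedman's formula is Power = Φ(√D × (1 − HR)/(1 + HR) − 1.96).
- HR 0.60: Φ(12.60 × 0.250 − 1.96) = 88.3%, against 87.5% stated.
- HR 0.635: Φ(12.73 × 0.2232 − 1.96) = 81.1%, against 80% stated.

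Schoenfeld's formula gives 89.6% and 82.4% with no loss, and 87.8% and 80.1% with an assumed 2% yearly loss. The event model therefore matches the protocol's own figures closely.

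**Step 2: events if the strategies are equal.** Hazard λ = −ln(0.80)/5 = 0.0446 per year. The mean event probability is 1 − (0.8 − 0.8^1.5)/(2.5λ) = 0.243. Expected events are 800 × 0.243 = 194.4.

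**Step 3: non-inferiority power at equality.** SE of the log hazard ratio = 2/√194.4 = 0.1434. The margin on the log scale is −ln(0.89) = 0.1165, or 0.81 SE. Power = Φ(0.1165/0.1434 − 1.645) = Φ(−0.83) = 20.3%.

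**Step 4: what must be observed.** Non-inferiority requires an observed medical/interventional HR of at most exp(0.1165 − 1.645 × 0.1434) = 0.887. Superiority requires at most exp(−1.96 × 0.1434) = 0.755. An observed HR of exactly 1.00 would carry a 90% interval of exp(±1.645 × 0.1434), or 0.79 to 1.27, which extends well past the margin of 1/0.89 = 1.12.

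**Step 5: other true effects.** HR is medical/interventional, with the interventional arm held at 20%.

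| True HR | Events | Non-inferiority power | Superiority power | Non-inferior but not superior | Non-inferior, given not superior |
|---|---|---|---|---|---|
| 1.00 | 194.4 | 20% | 2.5% | 18% | 18% |
| 0.90 | 185.9 | 45% | 11% | 34% | 38% |
| 0.80 | 177.1 | 73% | 32% | 41% | 61% |
| 0.75 | 172.6 | 84% | 47% | 37% | 70% |
| 0.60 | 158.8 | 99% | 90% | 9% | 90% |

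**Step 6: what would be needed.** Events for 80% power at equality: 4 × (1.645 + 0.842)² / 0.1165² ≈ 1,821. Divided by 0.243, this is about 7,500 patients. Conversely, 194.4 events give 80% power at equality only for a margin of exp(−2.487 × 0.1434) = 0.70.

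**Step 7: sensitivity at equality.**
- Five-year rate of 12.5% to 30% in both arms: 16% to 26%.
- Assumed yearly loss of 1% to 3%: 19% to 20%.
- Follow-up cut at 5 years (160 events): 18%.
- Every one of the 800 patients having an event: 50%.
- Absolute scale, 2-point margin, 20% in both arms: 17%.

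**The case against.** The strongest reply is that the sentence names no power and no true effect, and that the protocol expects medical management to be better. At its design hazard ratios of 0.60 and 0.635, non-inferiority power is 99% and 98%. Among trials that narrowly miss superiority at those effects, about 90% and 87% would still show non-inferiority. Read as a safety net for a near miss, the sample size does serve.

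Part of this stands. The fault is a misleading verbal assurance, not a wrong printed number, and the margin is internally consistent (1 − 0.8^0.89 = 18.0% against 20%). The ceiling of about 41% in the fifth column of the table must also be read with care: at strong effects it falls because superiority succeeds, and the conditional chance in the last column keeps rising.

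It does not rescue the sentence. The fallback runs only when superiority has failed, which is uncommon at HR 0.60 (about 10%). It matters most when the strategies are similar, and equality is the customary reference for a non-inferiority claim. There the test fails about four times in five. Power reaches 80% only if medical management is truly better by about 23% (HR near 0.77).

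Two further cautions are fair. The protocol draws no conclusion from a failed non-inferiority test, so the misreading is a risk, not something it instructs. Superiority of intervention could still emerge from the two-sided test, and Aim 1.2 gives a separate result, so the trial is not silent if Aim 1.1b fails. A SAP may give power assumptions for the fallback, but the Précis would still assert a property that the design lacks.

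**Conclusion.** The concern holds. With 800 patients, the non-inferiority test as specified has about 20% power at true equality, 45% at a medical/interventional hazard ratio of 0.90 and 73% at 0.80. The figure at equality rests on exponential survival, uniform entry and no loss to follow-up. Changing the loss assumption or the length of follow-up moves it by only a point or two, and event rates from 12.5% to 30% keep it between 16% and 26%. No event rate brings it above about 50%. The statement in the Précis is wrong as written and concerns an aim listed under the primary hypothesis, so it must be corrected.

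**What to change.** Delete the sentence "This sample size will support a test of non-inferiority if the medical management is not superior to interventional therapy" from the Précis. In its place, and in the hypothesis paragraphs after section 1.2:

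- State the power of the non-inferiority test with its assumed true medical/interventional hazard ratio: about 20% at 1.00, 45% at 0.90 and 73% at 0.80. Name the assumptions behind these figures (exponential survival, uniform entry, no loss), or recompute them with the sponsor's own loss assumption.
- State that failure to show non-inferiority is inconclusive and is not evidence that medical management is inferior, and that the hazard ratio with its confidence interval will be the reported result.

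Enlarging the trial is not a realistic remedy. Section 4.3 puts the centres' eligible volume at 650 to 1,000 patients a year, so 7,500 patients would take 7.5 to 11.5 years (7,500/1,000 to 7,500/650) even if every eligible patient enrolled.

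The cost is protocol wording only. Sample size, margin, significance level and conduct are unchanged; one stated property of the design becomes less favourable.

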1. SPECIFIC AIMS

Current interventional therapy for brain arteriovenous malformations (BAVMs) is varied and includes endovascular procedures, neurosurgery, and radiotherapy alone and in combination, largely dependent on the decisions of the local clinical team. All of these interventional therapies are administered on the assumption that they will decrease the risk of initial or subsequent hemorrhage and lead to better long-term outcomes. Despite these laudable goals, the literature contains almost no reference to the outcome for medical management before or after hemorrhage, or for intervention outcome for unruptured BAVMs. Published reports of interventional therapy outcome typically have blended the bled and non-bled cohorts together as if their risk for lesion-related morbidity and the response to intervention is expected to be the same.

Although no clinical trial data exist on the effect of interventional therapy even after BAVM hemorrhage, the most contentious issue at present is whether interventional therapy should be considered for those increasingly being discovered incidentally by brain imaging, with lesions that have not bled. Recent data from our institution on BAVM patients who presented without bleeding raises the possibility that interventional therapy may be detrimental compared with medical management. Among possible reasons may be that interventional therapy destabilizes the lesion toward hemorrhage. Furthermore, there is disappointing evidence that contradicts prior assumptions that hemorrhage associated with BAVM treatment lie in functionally-inert tissues, and, therefore, are less disabling. It appears that the disabilities associated with such events are equivalent to and possibly worse clinically than that seen with spontaneous BAVM hemorrhages, which still have a relatively low likelihood of occurring in the foreseeable future.

1.1 Primary Aims

The *primary hypothesis* of this randomized clinical trial is that medical management improves long-term outcomes of patients with unruptured BAVMs compared to interventional therapy (with endovascular procedures, neurosurgery, or radiotherapy, alone or in combination). The primary outcome is the composite event of death from any cause or stroke (hemorrhage or infarction confirmed by imaging). Functional outcome status will be measured by the Rankin Scale, a widely-used outcome measure for stroke. There are three specific aims associated with the primary hypothesis:

Specific Aim 1.1a To determine whether medical management is *superior* to interventional therapy for preventing the composite outcome of death from any cause or stroke (hemorrhage or infarction confirmed by imaging) in the treatment of unruptured BAVMs.

Specific Aim 1.1b If medical management is not superior to interventional therapy, to determine whether medical management is *not inferior* to interventional therapy for preventing the composite outcome of death from any cause or stroke (hemorrhage or infarction confirmed by imaging) in the treatment of unruptured BAVMs.

Specific Aim 1.2 To determine whether treatment of unruptured BAVMs by medical management decreases the risk of death or clinical impairment (Rankin Score ≥ 2) at 5 years post-randomization compared to interventional therapy.

1.2 Secondary Aims

A number of Secondary Aims are planned in support of the primary hypothesis to answer the following questions:

- 1) Is there a difference in quality of life between interventional therapy and medical management?
- 2) Is there a difference in mortality between interventional therapy and medical management?
- 3) Is there a difference in quality-adjusted survival between medical management and interventional therapy?
- 4) Is there a difference in the incidence of adverse events, such as cerebral hemorrhage and infarction, between interventional therapy and medical management?
- 5) What are the costs associated with each treatment (medical management and interventional therapy); and if medical treatment is not superior, but also not inferior to interventional therapy what are the cost-effectiveness implication of choosing one therapy over another?
- 6) Does any benefit of medical management or interventional therapy depend on BAVM size?
- 7) Does any benefit of medical management or interventional therapy depend on BAVM location?
- 8) Does any benefit of medical management or interventional therapy depend on venous drainage pattern?
- 9) Does any benefit of medical management or interventional therapy depend on age at randomization?
- 10) Does any benefit of medical management or interventional therapy depend upon the length of time the AVM was known?
- 11) Is there a difference in the risk of the composite event of death from any cause or stroke between prophylactic treatment modalities (i.e. endovascular procedures, neurosurgery, and radiotherapy)?
- 12) Among patients treated by interventional therapy, is there a relationship between the completeness of eradication of the BAVM and the composite event of death from any cause or stroke?
- 13) Among patients treated by interventional therapy, is there a relationship between the Spetzler-Martin grading scale and the composite event of death from any cause or stroke?

The *primary null hypothesis* is that there is no difference between medical management and interventional therapy in the time to stroke or death from any cause. The null hypothesis will be tested against the alternative hypothesis that there is a difference between treatments with a two-sided 0.05 level log-rank test. With a plan to enroll 800 patients, the test will have 87.5% power to detect a risk reduction of 40% (hazard ratio of 0.60), and 80% power to detect a risk reduction of 36.5% (hazard ratio of 0.635). These hazard ratios correspond to an absolute decrease in 5-year event rates of 7.5% and 6.7% respectively for medical management, from an assumed 5-year event rate of 20% for interventional therapy.

If the null hypothesis is not rejected, a test of non-inferiority of medical management compared to interventional therapy will be performed. The null hypothesis for the test of non-inferiority is that the hazard ratio for the composite event of death from any cause or stroke for interventional therapy compared to medical management is less than 0.89 (an 11% reduction in risk for interventional therapy). Thus, the null hypothesis that medical management is inferior will be rejected, and non-inferiority claimed, if the reduced risk of interventional therapy compared to medical management is less than the non-inferiority margin of 11% (hazard ratio ≥ 0.89) based on a one-tailed 0.05 level test. An 11% reduction in risk corresponds to an absolute difference in 5-year event rates of 2%.

The *secondary hypothesis* to be tested is that early intervention decreases the risk of death or clinical impairment at 5 years post-randomization. Death in this young, and otherwise healthy, population is a rare event. The primary hypothesis has been constructed to be inclusive of all strokes that occur during the course of the trial (thereby averting judgment about severity), while the secondary hypothesis concentrates only on those events associated with impairment.

2. BACKGROUND

2.1 Rationale

With the emergence of new non-invasive imaging techniques, there has been a substantial increase in the incidental detection of non-ruptured BAVMs. These BAVMs are being treated in a variety of ways, including medical management, endovascular procedures, neurosurgery, or radiotherapy. The widespread diffusion of these various treatment approaches is partially driven by the existence of variations in the perception about the risks of rupture and how devastating such events would be. The increased treatment rate of non-ruptured BAVMs consumes a considerable amount of health resources. With an annual incidence in the US of nearly 3000 cases, and treatment costs in the range of \$50,000 to \$100,000 per patient, widespread utilization of early intervention would amount to an expenditure of between \$150 million and \$300 million per year. Thus, the choice between early interventional therapy and medical management involves making a critical trade-off between avoiding the upfront risks and cost of an early intervention and possibly mitigating the long-term risks and costs associated with medical management. These trade-offs have not been adequately addressed in the clinical literature.

